Phase I (N=101) has concluded and a manuscript is in submission. In this study, W-SUDs was feasible to deliver, engaging, and acceptable; and associated with significant improvements in substance use, confidence, cravings, depression, and anxiety. Study attrition was high.

The supplemental study (W-C19) is a randomized control trial with a wait-list control condition. This study aimed to expand understanding of W-SUDs' performance among users experiencing SUDs whilst contributing to our overall understanding of COVID-19's impact upon this population. The intervention had concluded with N=180 participants enrolled. Experiencing worsened mental health symptoms during COVID-19 was associated with more substance use problems and depression and anxiety symptoms. Pandemic disruptions may exacerbate preexisting substance use problems.

Phase II will evaluate the efficacy of W-SUDs in a large scale RCT relative to an education-only control condition. Primary outcomes will be measures of the quantity and frequency of substance use including, number of substance use occasions, heavy drinking days (if applicable), percent days abstinent. Additionally, phase II will evaluate whether W-SUDs results in a greater reduction in substance-related problems than Education Only control and explore: Does engagement with W-SUDs, relative to education-only control (a) improve symptoms of depression and anxiety (b) improve work productivity (i.e. reduce presenteeism/absenteeism), (c) reduce cravings, (d) improve situational confidence. Phase II will also allow the team to learn more about the population interested in digitally delivered interventions.

Impact

Immediate access to a digital therapeutic in a resource constrained, social distance healthcare ecosystem amidst growing psychological challenges in this already vulnerable and underserved population.

Elements of our W-C19 program have already been integrated into W-SUDs because we felt that it was timely and appropriate to address users' concerns about the pandemic and demonstrated that Woebot was 'intelligent' to the current crisis.

c) **Explain why human subjects must be used for this project. (i.e. purpose of study is to test efficacy of investigational device in individuals with specific condition; purpose of study is to examine specific behavioral traits in humans in classroom or other environment)**

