Woebot for Substance Use Disorders Phase 2 RCT: Digitally Delivered Intervention for
Reducing Problematic Substance Use

NCT ID: 04925570

March 17, 2023

Descriptive statistics (means, frequencies) will be run to describe the sample, and the balance achieved by the randomization, and to examine ratings of program feasibility and acceptability. Missing data on individual survey items is anticipated to be minimal. As needed, individual participants' average score values may be imputed when missing individual items on a scale (e.g., PHQ-8). For the outcomes of interest, the target estimand is the intent to treat on the study population with no loss to drop-out of the study (i.e., this estimand incorporates noncompliance with the randomization's assigned level of intervention). We will examine predictors of study retention. Generalized Linear Models (multivariable models) will test for group differences in changes in the primary outcome and secondary outcomes. The dependent variables will be baseline to EOT (and baseline to 1-month follow-up) change scores. The models are used to adjust for baseline group differences and will apply weights to adjust for correlates of study retention. Participant weights will be calculated as the inverse of predicted probability values from a logistic regression model predicting EOT (and 1-month follow-up) retention.

Between-subject differences in baseline variables may be substantial (e.g., baseline number of substance use occasions) so the models will use change from baseline to a given time point (e.g., number of substance use occasions at EOT minus the number of substance use occasions at baseline). This trial, while not an exact replication, extends previous work with a waitlist control where the primary outcome was the change in baseline to EOT in substance use occasions. Thus, we separately analyze changes (a) from baseline to EOT, and (b) from baseline to 1-month.

Correlations also will be examined between W-SUDs engagement metrics and change in primary and secondary outcomes in the treatment group. Additionally, a per-protocol analysis will be limited to treatment participants who use W-SUDs at least 4 of 8 weeks and control participants who view at least half of the online psychoeducational fact sheets.

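### The primary test is never designated: the protocol lists several primary outcomes, the SAP tests one it does not name at two unranked time points, and no alpha or success rule is stated

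*Protocol*

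**What the plan says.** Protocol section 1(b), on Phase II, gives the primary outcomes in the plural: "Primary outcomes will be measures of the quantity and frequency of substance use including, number of substance use occasions, heavy drinking days (if applicable". The third item follows directly: "heavy drinking days (if applicable), percent days abstinent". The list is open-ended, one member is conditional, and no time point is attached. The next aim is comparative too: "phase II will evaluate whether W-SUDs results in a greater reduction in substance-related problems than Education Only control".

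The SAP uses the singular: "Generalized Linear Models (multivariable models) will test for group differences in changes in the primary outcome and secondary outcomes". It does not say what that outcome is. On timing it says "The dependent variables will be baseline to EOT (and baseline to 1-month follow-up) change scores" and later "Thus, we separately analyze changes (a) from baseline to EOT, and (b) from baseline to 1-month".

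Number of substance use occasions at EOT appears twice in the SAP. Once it is the example of how a change score is formed: "number of substance use occasions at EOT minus the number of substance use occasions at baseline". Once it describes another trial: "previous work with a waitlist control where the primary outcome was the change in baseline to EOT in substance use occasions". Heavy drinking days and percent days abstinent do not appear in the SAP.

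Elsewhere in the protocol, section 2(a) links significance testing to change from baseline to EOT. Section 2(c) adds that sustained change between weeks 8 and 12 will be observed as well. Section 1(a) describes the trial as fully powered and as meant to validate the product.

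**The concern.** An efficacy trial needs one identifiable test, or a stated rule over several tests, that decides whether it succeeded. Here the two documents disagree on how many primary outcomes there are, and neither fixes the outcome and the time point together.

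Suppose W-SUDs shows a benefit on percent days abstinent but not on occasions. Under the protocol's list this could be reported as a primary result. Under the SAP's single outcome, if that is occasions, it could not. A benefit at 1 month but not at EOT is open in the same way. Nor can the claim of full power be tied to any particular outcome.

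**Working it through.** **What the plan supplies.** Three named primary outcomes (protocol 1(b)); one unnamed primary outcome and two time points (SAP); N=400 (protocol 8(a)). The supplied text gives no alpha, sidedness, power, effect size, standard deviation or planning dropout rate, so N=400 cannot be reproduced, and nothing here says it is right or wrong.

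**Assumptions.** Two-sided 5% per test (critical value c = 1.960), jointly normal test statistics, a common correlation r, and 80% power per test where power is needed. None of these comes from the documents.

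**Rule A: one designated test.** The false-positive rate is 5%, or 1.0 times nominal.

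**Rule B: any one significant primary test counts.** With k independent tests, which is the maximum for jointly normal statistics, the rate is 1 − 0.95^k:

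- k = 2: 1 − 0.9025 = 9.75%
- k = 3: 1 − 0.8574 = 14.3%
- k = 6: 1 − 0.7351 = 26.5%

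With common correlation r, the rate is 1 − ∫ φ(u) [Φ((c − √r·u)/√(1−r)) − Φ((−c − √r·u)/√(1−r))]^k du:

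| Tests | Correlation | Rate | Multiple of 5% |
|---|---|---|---|
| One outcome, two time points (k = 2) | 0 (maximum) | 9.75% | 1.95 |
| | 0.5 | 9.1% | 1.8 |
| | 0.7 | 8.3% | 1.7 |
| | 0.9 | 7.0% | 1.4 |
| Three outcomes, one time point (k = 3) | 0 (maximum) | 14.3% | 2.85 |
| | 0.5 | 12.5% | 2.5 |
| | 0.8 | 9.8% | 2.0 |

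A correlation of 0.5 is a natural reference for the two time points because both change scores subtract the same baseline. With equal variances and equal correlation ρ among the three visits, and no baseline adjustment, the correlation of the two changes is (1 − 2ρ + ρ) / (2(1 − ρ)) = 0.5.

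For all six combinations, 26.5% is only an upper bound. Simulation with product correlation (2,000,000 draws) gives 21.9% when the correlations across outcomes and across times are both 0.5, and 14.9% when both are 0.8.

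**Rule C: all listed primaries must be significant.** Type I error is at most 5%. With effect/SE δ = 1.960 + 0.842 = 2.802 for each test, power is ∫ φ(u) [Φ((δ − c + √r·u)/√(1−r))]^k du:

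- k = 3: 61.1% at r = 0.5, 68.7% at r = 0.8
- k = 2: 68.7% at r = 0.5, 71.3% at r = 0.7

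**Splitting alpha equally instead.** Power of each test:

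- two tests: Φ(2.802 − 2.241) = 71.2%
- three tests: Φ(2.802 − 2.394) = 65.8%

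**The case against.** The best reply is that occasions at EOT is plainly what is meant. It is the SAP's worked example, it was the primary outcome of the waitlist trial this study extends, and it is the only one of the protocol's three measures that the SAP names. The SAP puts the 1-month analysis in brackets and lists it second, and protocol 2(a) and 2(c) point the same way. On that reading there is no inflation. Nor does any passage say that one significant result among several would be enough.

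Much of this stands. The lean towards EOT is real, so the time-point half of the problem is weaker than the outcome half, and the inflated rates apply only under a rule the documents do not state. But a lean is not a designation. The SAP's only definition of a primary outcome belongs to another trial, which it says this one does not exactly replicate, and the sentence that follows gives both time points without preferring one. None of it removes the primary status that protocol 1(b) gives to the other two measures.

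Protocol 2(g) calls the 30-day follow-up the endpoint, but its next sentence shows that this means the end of participation. It is not relied on here as a rival time point.

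Parts of the protocol are redacted or removed and its section 16 attachments were not supplied, so the absence of a rule is established only for the text available. The SAP shows no redaction, and a designation belongs there.

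**Conclusion.** The concern holds and must be fixed. The protocol and SAP conflict on the number of primary outcomes, the SAP does not designate its own, and the supplied text contains no alpha, testing order or success criterion.

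The effect on error ranges from none, under the reading the text favours or under an all-must-succeed rule, up to ceilings of 1.95 times nominal on the SAP's single outcome and 2.85 times on the protocol's list at one time point. Those ceilings assume independence. At correlation 0.5 the multiples are about 1.8 and 2.5. Under an all-must-succeed rule the cost is power instead. Alpha, correlations, per-test power and the success rules are all assumptions. The missing designation itself depends on none of them.

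**What to change.** Before outcomes are analysed by arm, amend both documents as follows.

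- State that the primary test is the between-arm difference in change in number of substance use occasions from baseline to EOT, at a stated alpha (for example two-sided 5%).
- Make heavy drinking days, percent days abstinent and every 1-month contrast secondary, alongside substance-related problems and the SAP's other secondary outcomes.
- For the secondary tests, give an order or adjustment that applies after the primary test, or label them as not controlled for multiplicity.
- Say which participants the heavy-drinking-days condition covers.
- Replace the open list in protocol 1(b) to match, and reword protocol 2(g) so that its endpoint clearly means the end of participation.

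Co-primary outcomes with a stated adjustment would also resolve the conflict, but at the power cost shown for splitting alpha. Occasions at EOT stays closest to the existing text and keeps the full alpha for one test.

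The cost is wording only. Data collection does not change and the amendment itself does not alter N=400, although the documents do not show whether 400 is enough for this outcome. The downside is that efficacy could not be claimed on another outcome or time point if the primary test is not significant.

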The purpose of this study is to test the efficacy of a mobile-application delivered substance use disorder intervention compared to an education only control group.

2. Study Procedures

Title : Woebot for Substance Use Disorders Phase 2 RCT: Digitally Delivered Intervention for Reducing Problematic Substance Use (SU sIRB) Short name: Anchor Study

Approval Period: 03/17/2023 - 05/11/2023

a) Please SUMMARIZE the research procedures, screening through closeout, which the human subject will undergo. Refer to sections in the protocol attached in section 16, BUT do not copy the clinical protocol. Be clear on what is to be done for research and what is part of standard of care.

Updated consent forms and HIPAA authorization will be uploaded before the start of recruitment. Ads, questionnaires, etc. will be uploaded for review before recruitment begins.

Recruitment will be a joint effort by Stanford University and Woebot Labs. Woebot may communicate the research opportunity through social media channels, and third party recruitment groups (e.g. Splash Clinical, Map & Story, Clara Health). The Stanford team may recruit through Qualtrics panels, ResearchMatch, listservs, and contact participants from previous research studies who are interested in future studies. Working with [name] research team at Stanford, the Woebot team will take part in mapping out message development for the intervention and Woebot's IT team will lead the app programming (including build and quality control/de-bugging). Woebot will collect user data via the Woebot app (automatic process), which will be provided to the Stanford team. The Woebot team will participate in disseminating the study findings via publications and presentations.

Participants from recruitment channels will go through and screening consent and eligibility screener, and if eligible, will be asked to participate in their randomized group for 8 weeks and answer questionnaires administered at the beginning, mid-intervention (4-week), end of intervention (8-week), and post intervention (12-week). Informed consent form will appear after screening eligible, and must be signed before the baseline survey can be accessed. Computer randomization will occur after the baseline survey, and instructions for their group will be sent out. Woebot will rely on Stanford University IRB for review of this study.

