Implementation of the VPN check is based on the guidelines presented in the following manuscript on <https://ssrn.com/abstract=3327274>

The IP address check can be done manually by study staff by uploading a CSV file of IP addresses onto IPhub.info. The study team proposes to check IP addresses on IPhub.info after a potential respondent passes the screening questionnaire, before the ICF is sent out. Respondents who do not pass this check will not be considered eligible for the study and will not receive an invite to the ICF.

The screening questionnaire will include a message about this check after the screening consent, and if screened eligible, a reminder that the IP address will be checked.

Protection against spamming:

Respondents who passed the screening questionnaire, but share an IP address with one or more respondents who passed screening, may be the same respondent using different emails. These respondents will not receive an invite to the ICF.

Protection against duplicates:

Respondents with the same email or phone number will not receive an invite to the ICF.

Title : Woebot for Substance Use Disorders Phase 2 RCT: Digitally Delivered Intervention for Reducing Problematic Substance Use (SU sIRB) Short name: Anchor Study

Approval Period: 03/17/2023 - 05/11/2023

Quality check before randomization:

If 20% or more of the responses answered in the baseline survey are "Prefer to not respond/Prefer to not answer", these respondents are not providing informative data for the study and can be removed from participation.

b) Explain how the above research procedures are the least risky that can be performed consistent with sound research design.

Given that the research aims to enroll a low-treatment seeking population, we do not envisage that participation in the study will be associated with elevated risk.

However, some risk is always present in studies that involve human participants.

Such risk may include the following:

Risk from breach of protected health information.

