Recruitment: For this study, Woebot Labs' may post study advertisements and recruit via their already active internet channels including Twitter (over 2,000 followers), LinkedIn (over 400 followers), and Facebook (over 16,500 followers). To supplement recruitment, Woebot Labs' may post on Craigslist, Nextdoor, Google Ads, and on Reddit through relevant subreddits with written permission from the subreddits' moderators. Woebot may email clinics. Woebot may also post physical flyers and the Stanford team may post on the Stanford Staffers listserv. The Stanford team may recruit from the WELL cohort via

Title : Woebot for Substance Use Disorders Phase 2 RCT: Digitally Delivered Intervention for Reducing Problematic Substance Use (SU sIRB) Short name: Anchor Study

Approval Period: 03/17/2023 - 05/11/2023

newsletter, with permission. Stanford staff may post in other listservs with permission. The Stanford team may recruit participants from other studies who have indicated interest in other studies. The team may use Qualtrics panels, ResearchMatch (online health research tool funded by NIH to match volunteers with studies), the Stanford COVID-19 directory to recruit, and other third party recruitment vendors (e.g. Splash Clinical, Map & Story, Clara Health).

In regards to their specific substance use behaviors over the previous month, 22% of users reported having 5 or more alcoholic drinks in a row within a couple of hours (i.e., binge use), and 5% endorsed using non-prescription drugs. Woebot Labs has used these channels for previous research participation invitations with success.

Minor editing changes may be made to recruitment materials to enhance clarity.

Participants will be asked for their age during the screener. If ineligible, they will be not be able to participate in the study. We will ask for date of birth in the questionnaire after the signed consent to confirm that the participant is not underage. This is standard best practice for use of the program and for other online research studies.

IRB modification 8/26/2022: Quality checks will be implemented prior to the ICF and before randomization. These quality checks include protection against bots, international respondents, spamming, and duplicates. Baseline survey respondents with 20% or more "Prefer not to answer" responses will not be randomized.

IRB modification 12/19/2022: DOB will be asked at each survey to verify identity.

h) Inclusion and Exclusion Criteria.

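### The 20% refusal check before randomisation does not protect the few baseline items behind the primary outcome, so someone who declines only those items can be randomised with no computable change score.

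*Protocol*

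**What the plan says.** **The check.** Protocol section 2(a), under the quality check before randomisation, begins "If 20% or more of the responses answered in the baseline survey are" marked as a preference not to answer, and concludes that "these respondents are not providing informative data for the study and can be removed from participation". Section 8(g), in the entry for the IRB modification of 8/26/2022, restates the threshold more firmly: baseline respondents at or above 20% prefer-not-to-answer "responses will not be randomized". Both apply the percentage to the survey as a whole.

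**Randomisation.** Section 2(a) also says "Computer randomization will occur after the baseline survey, and instructions for their group will be sent out". It attaches no condition about which items must be complete, and the eligibility list in section 8(h) adds none.

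**The outcome.** Section 1(b): "Primary outcomes will be measures of the quantity and frequency of substance use including, number of substance use occasions", together with heavy drinking days where relevant and the percentage of days abstinent.

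**The analysis.** SAP, first paragraph: "The dependent variables will be baseline to EOT (and baseline to 1-month follow-up) change scores". The second paragraph gives the definition by example: "number of substance use occasions at EOT minus the number of substance use occasions at baseline". The first paragraph also allows a participant's own average to fill missing items within a scale (PHQ-8 is the example), weights by the inverse predicted probability of retention at EOT and at 1 month, and targets an intent-to-treat estimand without loss to drop-out.

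**The concern.** The stated purpose of the check is to keep out people whose baseline data are uninformative. For the primary analysis, the one indispensable piece of baseline data is the use count that is subtracted at each later visit. A whole-survey percentage gives that count no more weight than any other item.

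If the count is refused, the change score cannot be formed at either time point, whatever the person reports later. The SAP offers no remedy. Averaging across a scale cannot supply a count that is wholly absent. The weights are built to represent people lost at follow-up, not people who return but lack a baseline value.

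Such a person takes one of the 400 places and can receive up to three further payments of $25 ($75), yet cannot enter the primary comparison. The problem can be prevented at the point where the sponsor already pauses to check baseline data.

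**Working it through.** The plan gives no figure to reproduce: the 20% is a rule, and neither document contains a power calculation. The check is therefore whether refusing only the primary-outcome items could reach 20%.

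**Inputs.** Protocol section 11(b) lists DAST-10 (10 items), DASE (12), MAST (22), SIP-AD (15), PHQ-8 (8) and SPS-6 (6). GAD-7 is taken as 7 from its name. The Quick Drinking Screen (QDS) is described by four drinking variables and is assumed to be 4 items. The instrument for use occasions is not identified, so one item is assumed where it is included. Section 8(i) uses selected DAST-10 and MAST items in the screener, so lists with and without those scales are shown.

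**List totals**
- All listed scales: 10 + 12 + 22 + 15 + 4 + 8 + 7 + 6 = 84
- Without MAST, plus one occasions item: 10 + 12 + 15 + 4 + 1 + 8 + 7 + 6 = 63
- Without MAST and DAST-10: 12 + 15 + 4 + 8 + 7 + 6 = 52, or 53 with the occasions item

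**Refusing only the primary-outcome items** (share = items declined / total items)

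| Declined | Total | Share |
|---|---|---|
| QDS, 4 | 84 | 4.8% |
| QDS, 4 | 52 | 7.7% |
| QDS + occasions, 5 | 63 | 7.9% |
| QDS + occasions, 5 | 53 | 9.4% |
| QDS + occasions, 5 | 63 + 100 unlisted | 3.1% |

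All are under half the threshold. Five refusals reach 20% only in a survey of 5 / 0.20 = 25 items or fewer. Those five items plus PHQ-8, GAD-7 and SPS-6 already make 5 + 8 + 7 + 6 = 26.

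**Sensitivity to the assumed item count.** On the shortest list there are 52 − 4 = 48 other items. With k primary-outcome items the share is k / (48 + k), which reaches 20% at k = 12 (12/60). The result holds for up to 11 such items, and for more if the survey is longer.

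**Refusing every substance-related scale**
- 84-item list: 10 + 12 + 22 + 15 + 4 = 63; 63/84 = 75.0%
- 52-item list: 12 + 15 + 4 = 31; 31/52 = 59.6%
- Smallest count tried (SIP-AD, QDS and one occasions item, with DASE counted as non-use): 20/53 = 37.7%

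These people meet the rule. They would fall below 20% only in surveys of more than 63 × 5 = 315, 31 × 5 = 155 or 20 × 5 = 100 items respectively.

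**Consequence, by assumed share m affected.** Analysable N = 400(1 − m), before any drop-out. Suppose N = 400 (200 per arm) gave 80% power at two-sided 5%. The standardised effect is then d = (1.960 + 0.842) × √(2/200) = 0.280, and power with n per arm is Φ(d√(n/2) − 1.960). The same is done for 90% power, with d = 0.324.

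| m | N | from 80% | from 90% |
|---|---|---|---|
| 1% | 396 | 79.6% | 89.7% |
| 2% | 392 | 79.2% | 89.4% |
| 5% | 380 | 78.0% | 88.5% |
| 10% | 360 | 75.7% | 86.8% |

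**The case against.** **The questionnaire is not in the documents.** Section 11(b) answers a question about protected health information and is not a stated baseline battery; its numbering skips 7 and 8. Nothing shows that the use-count items offer a refusal option. If they are forced-response, the gap does not arise. This stands as a limit on how often the problem could occur. It does not supply the missing rule.

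**Few people would do this.** Entrants have endorsed a substance use concern and scored 2 or more on CAGE-AID, and the SAP expects little item-level missing data. Refusing only the counts after that may be rare. This also stands, and it is why the power loss is put as small.

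**The check was meant for something else.** It sits beside the bot, spam and duplicate checks, and it does work as a general screen. But its stated rationale is informative data, and the primary outcome is the natural place to apply that.

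**Readings that go too far.** A reader might infer that someone who declines every substance-use item slips through. The listed counts do not support that: such a person refuses about 38% to 75% of the items and is flagged. A reader might also infer that refusing all of SIP-AD, or QDS plus DASE, escapes the rule and costs a primary outcome. On the 52-item list these are 15/52 = 28.8% and 16/52 = 30.8%, so both are caught, and section 1(b) treats substance-related problems and confidence separately from the primary outcomes. Finally, a reader might infer a biased treatment comparison. Refusal occurs before randomisation and cannot depend on arm, so leaving these people out does not in itself unbalance the groups. Nor is it drop-out in the SAP's sense. Because the SAP does not define retained, how the weights would treat them is unstated.

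**Conclusion.** The point holds in a limited form. The whole-survey threshold leaves the primary-outcome items unprotected, and a respondent who declines only those items can be randomised with no change score at EOT or 1 month and no stated handling. The refusal share is 4.8% to 9.4% on the lists above and lower in a longer survey.

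This rests on three assumptions: four QDS items with or without one occasions item (it survives up to 11 primary-outcome items on the shortest list), a refusal option on those items, and the section 11(b) scales as a rough guide to the baseline survey. The number affected is not in the documents. The cost is analysable sample and precision: 4 of 400 participants for each 1% affected, and about 2 percentage points from an assumed 80% power if 5% are affected.

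Separately, the two statements of the 20% rule differ: section 2(a) permits removal and section 8(g) requires it. As written, even a respondent who reaches the threshold is not certain to be excluded. This is a cheap improvement to the plan, not a threat to its validity.

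**What to change.** Add to sections 2(a) and 8(g): *A respondent is randomised only if the baseline items needed to compute the primary outcome(s) applicable to them have a substantive answer; the 20% rule applies in addition.* Name those items, since section 11(b) does not identify the source of the use-occasions count. The word applicable matters because heavy drinking days do not concern every participant. Programme the condition as a logic check before the randomisation step. If the use items are already forced-response, one sentence saying so is enough.

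In the same edit, reconcile the permissive wording in section 2(a) with the mandatory wording in section 8(g).

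**Cost.** One eligibility sentence and one survey-platform check. A few respondents would be turned away after completing the baseline survey and would need replacing. People unwilling to report their use would not be represented in the trial, but the change-score analysis cannot include them either.
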